#### 11.4 Toxicity monitoring

A sequential probability ratio test (SPRT) will be used to provide a monitoring boundary for stopping the study in case there is moderate evidence that the proportion of extended grade 4 toxicities is 20% as opposed to the permitted rate of 5%. This monitoring boundary will be used to evaluate the toxicity data after every patient. The SPRT is based on testing two simple hypotheses on the basis of the likelihood ratio. The likelihood function for a binary toxicity outcome is binomial and the log likelihood ratio will be used to determine the relative evidence in favor of two hypothesized prolonged grade 4 toxicity rates,  $p_1=0.2$  and  $p_2=0.05$ . The

likelihood ratio is:

$$\text{Likelihood ratio (For } p_1 \text{ vs } p_2 \mid \text{Data)} = \frac{\Pr(\text{data} \mid \theta = 0.2)}{\Pr(\text{data} \mid \theta = 0.05)} = \frac{\theta^x (1 - \theta)^{N-x}}{\theta^x (1 - \theta)^{N-x}}$$

where  $N=36$  and  $x$  is the number of toxicities observed. We will stop the study if there is moderate evidence,  $LR \geq 8.0$ , that the proportion of prolonged grade 4 toxicities is 20% versus 5%. The stopping boundary corresponding to this LR is given below. If the number of toxicities falls above the line any point along the study, the study will be stopped. Table 1 gives the observed number of prolonged toxicities for which this boundary would be crossed after each patient accrued ( $N$ ). The rate of erroneously stopping the study using this boundary is approximately  $1/8$  or  $0.125$ .

[figure not shown]

Table 1. Observed number of prolonged toxicities (Tox) where SPRT boundary would be crossed after each patient accrued ( $N$ ).

N	1	2	3	4	5	6	7	8	9	10	11	12	13	14	15	16	17	18
Tox	2	2	2	2	2	2	3	3	3	3	3	3	3	3	3	4	4	4

N	19	20	21	22	23	24	25	26	27	28	29	30	31	32	33	34	35	36
Tox	4	4	4	4	4	4	5	5	5	5	5	5	5	5	5	6	6	6

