Unrelated Unlikely	Not Required	Not Required	Not Required	10 Calendar Days	Not Required	10 Calendar Days	Not Required	10 Calendar Days	10 Calendar Days
Possible Probable Definite	Not Required	10 Calendar Days	Not Required	10 Calendar Days	10 Calendar Days	10 Calendar Days	Not Required	24-Hour; 5 Calendar Days	10 Calendar Days

 Adverse events with attribution of possible, probable, or definite that occur greater than 30 days after the last dose of treatment with an agent under a CTEP IND require reporting as follows:

CTEP-AERS 24-hour notification followed by complete report within 5 calendar days for:

- Grade 4 and Grade 5 unexpected events

CTEP-AERS 10 calendar day report:

- Grade 3 unexpected events with hospitalization or prolongation of hospitalization
- Grade 5 expected events

 Although a CTEP-AERS 24-hour notification is not required for death clearly related to progressive disease, a full report is required as outlined in the table.

December 15, 2004

**Note: All deaths on study must be reported using expedited reporting regardless of causality. Attribution to treatment or other cause should be provided.**

- Expedited AE reporting timelines defined:
  - “24 hours; 5 calendar days” – The investigator must initially report the AE via CTEP-AERS within 24 hours of learning of the event followed by a complete CTEP-AERS report within 5 calendar days of the initial 24-hour report.
  - “10 calendar days” - A complete CTEP-AERS report on the AE must be submitted within 10 calendar days of the investigator learning of the event.
- Any medical event equivalent to CTCAE grade 3, 4, or 5 that precipitates hospitalization (or prolongation of existing hospitalization) must be reported regardless of

attribution and designation as expected or unexpected with the exception of any events identified as protocol-specific expedited adverse event reporting exclusions.

- Any event that results in persistent or significant disabilities/incapacities, congenital anomalies, or birth defects must be reported via CTEP-AERS if the event occurs following treatment with an agent under a CTEP IND.
- Use the NCI protocol number and the protocol-specific patient ID provided during trial registration on all reports.

Expedited Adverse Event Reporting Exclusions – Not Applicable

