### 10.4 Data and Safety Monitoring

Scheduled meetings will take place monthly and include the protocol principal investigator, study coordinators, research nurses, and, when appropriate, the collaborators, sub-investigators, and biostatistician involved with the conduct of the protocol. During these meetings the investigators will discuss matters related to: safety of protocol participants, validity and integrity of the data, enrollment rate relative to expectation, characteristics of participants, retention of participants, adherence to protocol (potential or real protocol violations), data completeness, and progress of data for secondary objectives such as surrogate markers. A review of all grade 3/4 toxicities will take place in each of the meetings as well as any delays in surgical procedure or in wound healing that may be contributed to study drug.

Quarterly reports will be sent to CTEP according to specified CTEP guidelines.

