### 10.5 CTEP Multicenter Guidelines

#### 10.5.1 Responsibilities of the Principal Investigator.

- The Principal Investigator will be the single liaison with the CTEP Protocol and Information Office (PIO). The Principal Investigator is responsible for the coordination, development, submission, and approval of the protocol as well as its subsequent amendments. The protocol must not be rewritten or modified by anyone other than the Principal Investigator. There will be only one version of the protocol, and each participating institution will use that document. The Principal Investigator is responsible for assuring that all participating institutions are using the correct version of the protocol.
- The Principal Investigator is responsible for the overall conduct of the study at all participating institutions and for monitoring its progress. All reporting requirements to CTEP are the responsibility of the Principal Investigator.

- The Principal Investigator is responsible for the timely review of Adverse Events (AE) to assure safety of the patients.
- The Principal Investigator is responsible for the review of and timely submission of data for study analysis.

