**NCI Protocol #: 7870**

with IL-2. The IL-2 dose level is 600,000 IU/kg, every 8 hours, IV. The current recommended dose of entinostat when administered as a single agent every second week continuously is 10 mg/m^2. The entinostat study dose levels are 1, 3 and 5 mg, every 2 weeks, PO with 3 mg chosen as the starting dose for this study. A DLT will be defined as extended grade 4 toxicity (duration of one week or more) during the first 45 days of treatment with the recommended dose being the highest dose at which 0 or 1 DLTs are observed. A DLT rate of  $\leq 33\%$  will be permitted for further evaluation in the Phase II portion of the study.

The first dose level will have a minimum of 3 patients treated (unless the first 2 patients experience dose-limiting toxicity(s) (DLT) before 3rd patient is enrolled. If a DLT occurs in 1 patient treated at the starting dose level, another 3 patients will be treated at this dose level. If DLTs occur in 2 patients in the first 6 patients, patients will be treated at a lower dose level (entinostat 1 mg PO every 2 weeks, dose level 0) and DLT will be evaluated similarly. If DLT occurs in 1/6 patients, dose level 1 will be considered the recommended Phase II dose.

If no DLTs occur at the starting dose level 1, 3 or 4 patients will be treated at the next dose level (level 2) with 5 mg PO every 2 weeks (wait 45 days for DLT assessment on first 2 patients before 3rd patient is enrolled). If no DLTs occur at dose level 2, this dose level will be recommended for the phase II portion of the study. If a DLT occurs in 1 patient at dose level 2, another 3 or 4 patients will be treated at this dose level. If DLT occurs in 2/6 patients at dose level 2, dose level 1 will be the recommended for the Phase II. If a DLT occurs in 1/6 patients, dose level 2 will be considered the recommended Phase II dose.

Patients who experience prolonged grade 4 toxicity (more than one week) and recover to  $\leq$  Grade 1 (or to pretreatment baseline level toxicity) may continue treatment at the next entinostat lower level. Once the entinostat has been dose reduced, patients must remain at the reduced dose for the remainder of the study. Patients may have their dose de-escalated twice before being removed from the trial. Patients will be allowed to remain on the therapy provided that they are tolerating the treatment and do not develop progressive disease. No dose de-escalation for IL-2 will be performed.

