## **11.7 Reporting and Exclusion**

### **11.7.1 Evaluation of toxicity**

All patients will be evaluable for toxicity from the time of their first dose of entinostat

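### The phase II toxicity stopping boundary counts only grade 4 events lasting about a week, so a rapid treatment-related death counts as a patient without toxicity

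*Combined protocol and SAP*

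**What the plan says.** Section 11.4 applies a sequential probability ratio test after every patient, up to N = 36. It stops when the likelihood ratio reaches 8, that is, when "there is moderate evidence that the proportion of extended grade 4 toxicities is 20% as opposed to the permitted rate of 5"%. Table 1 turns this into counts. Section 11.1 describes the rule in the same terms, and its event is extended grade 4 toxicity.

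The length of the event has to be taken from other sections. In Section 11.2, "A DLT will be defined as extended grade 4 toxicity (duration of one week or more) during the first 45 days of treatment". Later in the same section the wording is "Patients who experience prolonged grade 4 toxicity (more than one week"). Section 11.4 uses both *extended* and *prolonged* and defines neither. Section 11.7.2 takes prolonged lymphocyte decrease out of the DLT definition. Nothing adds death to it.

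On the denominator, Section 11.7.1 says "All patients will be evaluable for toxicity from the time of their first dose of entinostat".

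Deaths and other events are handled elsewhere:

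- Section 10.3.1 (phase 2 reporting): "All deaths on study must be reported using expedited reporting regardless of causality".
- Section 10.4 (monthly meeting): "A review of all grade 3/4 toxicities will take place in each of the meetings".
- Section 10.5.1: "The Principal Investigator is responsible for the timely review of Adverse Events (AE) to assure safety of the patients".

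On operating characteristics, Section 11.4 says only that "The rate of erroneously stopping the study using this boundary is approximately" 1/8, or 0.125.

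**The concern.** Crossing Table 1 is the only numerical trigger for stopping phase II for toxicity in the public text. The DLT counts in Sections 4.1 and 11.2 govern phase I dose selection, and Section 5.6 concerns individual patients. A trigger that requires a grade 4 event to last about a week favours events that the patient survives that long. Several items on the Section 5.6 list (coma, life-threatening sepsis, tamponade, bowel perforation) need not last a week before death.

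Such a death is not neutral to the rule. The patient is evaluable for toxicity and has no counted event, so the death moves the statistic towards the acceptable rate. A cluster of toxic deaths could therefore leave the boundary uncrossed, while a few week-long grade 4 events that resolve would cross it.

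**Working it through.** **Inputs.** Rates of 20% and 5%, stopping at a likelihood ratio of 8 or more, Table 1 and the stated 1/8 are from Section 11.4. The sample size of 36 is from Section 11.3. The documents give no toxic-death rate, so a range is assumed.

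**1. Reproducing Table 1.** Each event multiplies the ratio by 0.20/0.05 = 4, and each non-event by 0.80/0.95 = 0.842. So

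LR(x, N) = 4^x × (0.80/0.95)^(N − x).

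The boundary is the smallest x with LR ≥ 8. For example, x = 2 at N = 6 gives 16 × 0.503 = 8.05, which stops. At N = 7 it gives 16 × 0.4235 = 6.78, so 3 events are needed. All 36 entries agree with Table 1: 2 for N = 1–6, 3 for 7–15, 4 for 16–24, 5 for 25–33 and 6 for 34–36. The boundary arithmetic is sound.

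**2. What an uncounted death does.** Assume no patient has a week-long grade 4 event.

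| Toxic deaths | As written | If counted |
|---|---|---|
| 2 in first 6 | x = 0, LR = 0.842^6 = 0.36, continue | x = 2, LR = 8.05, stop |
| 4 in first 20 | x = 0, LR = 0.842^20 = 0.032, continue | x = 4, LR = 256 × 0.842^16 = 16.4, stop |

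As written, the second case favours the acceptable rate by about 31 to 1 (1/0.032).

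**3. Exact stopping probabilities of Table 1.** These come from a patient-by-patient binomial recursion: carry forward the probability of each count below the boundary, and remove the probability that reaches it.

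| True event rate | P(stop within 36) |
|---|---|
| 5% | 0.074 |
| 6% | 0.114 |
| 7% | 0.163 |
| 8% | 0.219 |
| 10% | 0.348 |
| 15% | 0.667 |
| 20% | 0.873 |

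The stated 1/8 is a valid upper bound for a rule that stops at LR ≥ 8, but this 36-patient boundary has a false-stop rate of 0.074. At 20%, expected enrolment is 15.4 over all trials, and the mean is 12.4 among trials that stop.

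**4. Effect of counting deaths.** Take prolonged grade 4 toxicity at 5% and deaths in other patients at an assumed rate d. If deaths count, the event rate is 0.05 + d. As written, it is 0.05 if no death follows a week of grade 4 toxicity, or 0.05 + d/2 if half do.

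| Assumed d | Deaths expected in 36 | As written, none preceded | As written, half preceded | Deaths counted |
|---|---|---|---|---|
| 1% | 0.36 | 7% | 9% | 11% |
| 2% | 0.72 | 7% | 11% | 16% |
| 3% | 1.08 | 7% | 14% | 22% |
| 5% | 1.80 | 7% | 19% | 35% |

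**The case against.** The rule is narrow for a reason. High-dose aldesleukin produces much short severe toxicity: Section 5.4 gives 56.8% grade 3/4 hypotension in cycle 1. A duration filter is therefore a reasonable way to look for toxicity added by entinostat. Deaths are also handled one at a time. Each needs expedited reporting whatever its cause, serious events go promptly to the principal investigator (10.3.1), sites notify their IRB and the coordinating office (Appendix D), and the monthly meeting covers participant safety. Four toxic deaths in 20 would go unanswered only if all these routes failed.

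The size of the effect also rests on assumed death rates; at 1% the change is only from 7.4% to 11.4%. Nor is the proposed composite a strong guard against deaths alone. One death never stops the study, and toxic deaths at 5% with no prolonged grade 4 events would stop it with probability only 0.074, because 5% is the permitted rate.

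Most of this stands as context. The filter is a sound choice for non-fatal events, and judgement-based stopping remains possible. But a filter meant to ignore brief, reversible toxicity gives no reason to score a death as an absence of toxicity. None of the other routes carries a threshold or feeds the boundary. The composite's weakness against deaths alone argues for justifying the 5% rate openly, not for leaving deaths out.

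**Conclusion.** The concern holds. As written, a treatment-related death without a grade 4 toxicity of about a week beforehand adds nothing to the phase II stopping count and lowers the likelihood ratio. That follows from the text and needs no assumption. The size does: across assumed separate-death rates of 1% to 5%, on top of 5% prolonged grade 4 toxicity, the chance of stopping is 11% to 35% if deaths count. As written it is 7% if no death is preceded by a week-long grade 4 event, and 9% to 19% if half are.

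Table 1 itself is correct. The false-stop statement gives an upper bound (0.125) as if it were the boundary's approximate rate (0.074), and the probability of stopping at 20% (0.87) is missing. The *extended*/*prolonged* wording, the 45-day window and the lymphocyte exclusion are points of clarification only, although with thresholds of 2 to 6 events a single disputed case can decide the outcome. The change should be made; the main uncertainty is how often such deaths would occur.

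**What to change.** In Section 11.4:

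- Define the monitored event once: extended grade 4 toxicity, lasting one week or more as in the Section 11.2 DLT definition, or any treatment-related grade 5 event. Use one term throughout and cross-refer to the lymphocyte exclusion in 11.7.2.
- State whether the 45-day DLT window applies to this rule.
- State that the 5% and 20% rates, and the error rates, refer to this composite.
- Call 1/8 an upper bound or give the exact 0.074, and add the 0.87 probability of stopping at a 20% rate.

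In Section 10.4, name grade 5 events alongside grade 3/4 in the monthly review.

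This is about five sentences, with no new data and no change to Table 1. The cost is that 5% becomes the permitted rate for a broader event and must be justified as such. If prolonged grade 4 toxicity runs at 5% and separate deaths add an assumed 1%, the chance of stopping rises from 7.4% to 11.4%.

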#### **4.1 Entinostat / aldesleukin administration and definition of Dose-Limiting Toxicity (DLT)**

Patients with metastatic renal cell carcinoma and no prior therapies will be eligible for treatment. One cycle of treatment (84 days) will consist of 2 courses of high dose aldesleukin 600,000 units/kg administered IV every 8 hrs. on day 1-5 and day 15-19 ( $\pm$  7 days) (maximum 28 doses), and entinostat orally (1-2 hrs. prior to aldesleukin infusion) given every 2 weeks starting on day-14, continuously. Entinostat is to be taken on an empty stomach, at least 1 hour before or 2 hours after a meal. Tumor response assessment will be performed on week 11 ( $\pm$  7 days). In the event of clinical benefit (stable disease or tumor shrinkage) patients will receive a second cycle of therapy.

Entinostat will continue every 2 weeks ( $\pm$  7 days dependent on adjustments necessary for aldesleukin dosing) until documented disease progression or 8 weeks following documented complete response. Patients with evidence of tumor shrinkage may receive up to 3 cycles of high dose aldesleukin therapy. Cycle 2 will start on or within 2 weeks following day 85 (or last day of cycle dependent on dosing adjustment) as in cycle 1. Cycle 3 can start within 2 weeks after completion of cycle 2. Patients with stable disease by RECIST V.1.0 criteria, but without evidence of tumor shrinkage after two cycles will receive only entinostat until disease progression is documented.

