In order to assess the effect of entinostat versus the combination on the proposed correlative pharmacodynamic parameters, initial treatment will be with entinostat monotherapy, followed by combination with high dose aldesleukin. The Phase I starting dose level of entinostat will be 3 mg PO every 2 weeks. The first dose level will have a minimum of 3 patients treated unless the first 2 patients experience dose-limiting toxicity(s) (DLT) before 3rd patient is enrolled. DLTs are defined as extended grade 4 toxicity (duration of one week or more) during the first 45 days of treatment. If DLTs occur in 1 patient treated at the starting dose level, a minimum of 3 or 4 patients will be treated at this dose level. If DLT occurs in more than 1 patient in the first 6 patients, patients will be treated at a lower dose level (entinostat 1 mg PO every 2 weeks, dose level 0) and DLT will be evaluated similarly. If DLTs occur in  $\leq$  1/6 patients, dose level 1 will be considered the recommended Phase II dose. If no DLTs occur at the starting dose level 1, 3 or 4 patients will be treated at the next dose level (level 2) with 5 mg PO every 2 weeks (wait 45 days for DLT assessment on first 2 patients before 3rd patient is enrolled). If no DLTs occur at dose level 2, this dose level will be recommended for the phase II portion of the study. If DLTs occur in  $\geq$  1 patient, another 3 patients will be treated at this dose level. If DLT occurs in  $\geq$  2 patients in the first 6 patients, dose level 1 will be the recommended for the Phase II. If DLTs occur in  $\leq$  1/6 patients, dose level 2 will be considered the recommended Phase II dose. Patients who experience extended grade 4 toxicity (duration of one week or more) and recover to  $\leq$  Grade 1 (or to pretreatment baseline level toxicity) may continue treatment at the next entinostat lower level. Once the entinostat has been dose reduced, patients must remain at the reduced dose for the rest of the study. Patients may have their dose de-escalated twice or up to dose level 0 before being removed from the treatment. Patients will be allowed to remain on the therapy provided that they are tolerating the treatment and do not develop progressive disease. No dose de-

escalation for aldesleukin will be performed.

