#### Secondary Objectives:

Secondary endpoints will be used to determine the effect of entinostat on progression free survival (PFS), survival, time-to tumor progression and parameters measuring immune response.

Failure rates will be used to compare the PFS, overall survival and time-to-tumor progression of metastatic RCC patients treated with high dose aldesleukin combined with entinostat to the historical failure rates of patients treated with high dose aldesleukin alone. The failure rate is estimated by dividing the number of events ( $d$ ) by the sum of the exposure time in the study

cohort:  $\lambda = d / \sum t_i$ . The 95% confidence interval is calculated as:  $\lambda \pm Z_{1-\alpha/2} \frac{\lambda}{\sqrt{d}}$ .

The historical PFS failure rate observed in the randomized trial of IL-2 reported by the Cytokine Working Group was 2.77 per person year (median PFS of 3 months). Patients eligible for this study are expected to be homogenous group with comparable prognostic characteristics. Enrollment is expected to be between 1 and 2 patients per month with an accrual period of 6 years and 12 months of follow-up. With a total of 34 events in 36 patients, the study would yield 79% power to detect a decrease in the PFS failure rate to 1.85 per person year of follow-up (an increase of 1.5 months in the median PFS compared to the historical median) at an alpha level of 0.1 (one-sided).

We do not expect that different doses of entinostat during the period off aldesleukin (maintenance) will affect the primary endpoint since objective responses have been rarely observed with single agent entinostat. We expect that the vast majority of patients will be able to tolerate the 10 mg maintenance dose if the phase II recommended dose in combination with aldesleukin is 5 mg. Should we observe discrepancies in the maintenance dose level of entinostat we will consider subgroup analysis to determine the secondary objective PFS in the different group of patients.

The toxicity of IL-2 when combined with entinostat will be further characterized following the phase II portion of this study. The exact binomial proportion for prolonged grade 4 toxicities with the 95% confidence interval will be given. Additional toxicity frequencies, proportions, and 95% CIs will be given by type and grade of toxicity.

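### The Phase II toxicity boundary counts patients accrued, so patients too early in treatment to show a week-long grade 4 toxicity count as toxicity-free and the rule acts late

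*Combined protocol and SAP*

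**What the plan says.** Section 11.4 compares a 20% rate of prolonged grade 4 toxicity with a permitted 5% and stops the study when the likelihood ratio reaches 8. On when to look it says: "This monitoring boundary will be used to evaluate the toxicity data after every patient". On how to enter the table it says: "Table 1 gives the observed number of prolonged toxicities for which this boundary would be crossed after each patient accrued". The title of Table 1 uses the same index. The likelihood has exponent x for toxicities and N − x for everyone else.

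Section 11.4 gives no observation period, no minimum follow-up and no pause in accrual. Section 11.7.1 makes patients evaluable for toxicity from their first entinostat dose. The Phase II summary in section 11.3 gives no period either: "The exact binomial proportion for prolonged grade 4 toxicities with the 95% confidence interval will be given".

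The only period attached to this event is in the Phase I DLT definition (sections 4.1 and 11.2): grade 4 toxicity of a week or more in the first 45 days of treatment. Phase I also waits 45 days on the first two patients at dose level 2 before enrolling the third. Section 4.1 says Phase II evaluations match Phase I but does not mention N or Table 1.

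On accrual, section 11.3 states: "Enrollment is expected to be between 1 and 2 patients per month with an accrual period of 6 years".

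**The concern.** Every accrued patient without a recorded event contributes a factor of 0.80/0.95 to the likelihood ratio and pulls it down. For a patient who has just started, that factor is unearned. Entinostat is "given every 2 weeks starting on day-14, continuously", and aldesleukin begins on day 1, about 14 days later. The event must then last a week. An aldesleukin-related event is therefore known about 21 days after the first dose at the earliest, and at 2 patients per month a new patient arrives about every 15 days.

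The error goes one way. Pending patients can cancel a stop but cannot cause one, so when toxicity is too high more patients are treated before the rule acts. Table 1 is the only numerical stopping rule in Phase II.

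**Working it through.** **Inputs from the documents.** Rates 0.05 and 0.20, threshold 8, maximum N of 36 and Table 1 (11.4); DLT period of 45 days and event duration of a week (4.1, 11.2); accrual of 1 to 2 per month, and the 6-year accrual period (11.3), which for 36 patients is 36/72 = 0.5 per month. A month is taken as 30.4 days.

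**Reproducing Table 1.** The boundary is the smallest x with x·ln(0.20/0.05) + (N − x)·ln(0.80/0.95) ≥ ln 8. This gives 2 for N = 1–6, 3 for 7–15, 4 for 16–24, 5 for 25–33 and 6 for 34–36. All 36 entries match. An exact recursion with outcomes known at once gives erroneous stopping of 0.074 at a true 5% rate, so the printed 0.125 holds as an upper bound. At a true 20% rate the stopping probability is 0.873 (0.869 before the 36th patient), with a mean of 15.4 treated.

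**One pending patient can remove a stop.** Two toxicities in 6 patients: LR = 16 × (0.80/0.95)^4 = 8.05, stop. Two in 7: LR = 16 × (0.80/0.95)^5 = 6.78, continue; Table 1 now asks for 3. At 2 per month patient 7 arrives about 15 days after patient 6, so an aldesleukin-related event in patient 6 cannot be known until N is at least 7.

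**Size under the 45-day period.** Assumed: even accrual; the period runs from the first entinostat dose; each event becomes known at a uniform time from day 21 to day 52 (45 + 7); the boundary is checked when an event becomes known. Simulation at a true 20% rate with N = accrued, at least 20,000 trials per case (error in the means about 0.1 to 0.2):

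| Accrual per month | Mean treated | Stop before 36th patient |
|---|---|---|
| No lag (exact) | 15.4 | 0.869 |
| 0.5 | 15.5 | 0.87 |
| 1 | 16.6 | 0.85–0.86 |
| 2 | 18.6 | 0.83 |

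**Hand check.** An exact recursion with a fixed number of pending patients gives means of 15.4, 17.1 and 18.8 for 0, 1 and 2 pending, or about 1.7 per pending patient.
- At 0.5 per month patients are 60.8 days apart, longer than 52 days. No one is pending, and the mean is 15.4.
- At 1 per month one further patient has entered if the event becomes known after day 30.4: (52 − 30.4)/31 = 0.70. Mean: 15.4 + 0.70 × 1.7 = 16.6.
- At 2 per month the number of further patients is 1 up to day 30.4, 2 up to day 45.6, then 3: (9.4×1 + 15.2×2 + 6.4×3)/31 = 1.9. Mean: 15.4 + 1.9 × 1.7 = 18.6.

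**Changed N.** Count a patient when the event is known, or at day 52 without one. At 2 per month and a true 20% rate, the probability of stopping before the 36th patient is about 0.87 and the mean treated about 16.6. At a true 5% rate, erroneous stopping is about 0.07 to 0.08, against about 0.05 with N = accrued.

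**The case against.** **The 45-day window may carry over.** Section 4.1 says Phase II evaluations are identical to Phase I. This is a fair reading of the event, and it is why the 45-day period is used here. It does not change what N is: both the text and the title of Table 1 say accrued.

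**Other safeguards exist.** Grade 4 and 5 events are reported on an expedited basis (10.3.1), section 5.6 removes individual patients, and monthly meetings review grade 3/4 toxicity (10.4). A careful team might wait for pending results. None of these sets a threshold on the rate or alters the denominator.

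**The example is a marginal one.** This stands: 8.05 is the smallest passing value in its band. At 1 per month an event in patient 6 known between day 21 and day 30 would still be judged at N = 6.

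**A reader might infer a much larger loss.** If events are spread evenly over all of cycle 1 (98 days from the first dose) or over two cycles (182 days), the mean treated at 2 per month is 21.1 or 24.9. The documents do not support those as headline figures. Cycle 1 aldesleukin ends about 33 days after the first entinostat dose, or about 40 with the 7-day allowance. Appendix C describes recovery within days of stopping, and a second cycle is given only with clinical benefit (4.1). The documents contain no onset data that would favour late events.

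**A reader might also infer that Table 1 or its 1/8 figure is wrong.** Neither is.

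**Conclusion.** The point holds, at modest size. Section 11.4 defines N as patients accrued, nothing elsewhere corrects it, and the effect is always toward late stopping. At a true 20% rate and the 45-day period, the average cost is negligible at 0.5 patients per month, about 1 patient at 1 per month (16.6 − 15.4 = 1.2) and about 3 at 2 per month (18.6 − 15.4 = 3.2). At 2 per month about 4 percentage points of stopping probability are also lost. Part of that cost is unavoidable, because even the right N cannot see an event before it happens: the change recovers about 2 of the 3 patients (18.6 − 16.6 = 2.0).

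The direction needs no timing assumption. The size does: it rests on even accrual and on events becoming known uniformly from day 21 to day 52. Later events would make the loss larger. This is worth correcting as a matter of safety wording; it does not undermine the design.

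**What to change.** In 11.4, keep Table 1 and the threshold of 8, and add: N counts patients who have had a prolonged grade 4 toxicity, or who have completed the Phase I DLT period (first 45 days, plus up to 7 days to confirm duration) without one. Each toxicity is counted as soon as it is known. Prolonged grade 4 toxicities that begin later are reported separately in the 11.3 summary. State also when a patient who leaves treatment early enters N; the 30-day safety contact in 4.3 is a natural point.

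Two wider versions are better avoided. Extending the event to all cycles and maintenance would apply the 5% and 20% rates to a cumulative event for which the protocol gives no basis. Clearing non-events only at the end of cycle 1 over-corrects when events come early: with 52-day events at 2 per month, stopping at a true 20% rate rises to about 0.90 and erroneous stopping at 5% rises from 0.051 to 0.117.

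The cost is one short paragraph and a cross-reference, with no change to sample size, dosing or data collection. The statistical price is the small rise in erroneous stopping shown above, to about the 0.074 that the boundary has with no lag.

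### Section 11.4 gives 1/8 as the toxicity boundary's false-stop rate; that is only its ceiling, and with prompt outcomes Table 1 attains 0.074

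*Combined protocol and SAP*

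**What the plan says.** Section 11.4 (Toxicity monitoring) sets a sequential rule that looks at the toxicity data after every patient, up to 36. The study stops if there is moderate evidence, defined as a likelihood ratio of at least 8, that "the proportion of extended grade 4 toxicities is 20% as opposed to the permitted rate of 5" percent. Table 1 turns this into counts. Its caption describes it as the "Observed number of prolonged toxicities (Tox) where SPRT boundary would be crossed after each patient accrued". The entries are 2 for N = 1 to 6, 3 for 7 to 15, 4 for 16 to 24, 5 for 25 to 33, and 6 for 34 to 36.

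The section gives one operating characteristic: "The rate of erroneously stopping the study using this boundary is approximately" 1/8 or 0.125. It does not call this a bound, and it gives no probability of stopping at the 20% rate.

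**The concern.** For any likelihood ratio, the probability of ever reaching k under the null hypothesis is at most 1/k. With k = 8 that is 0.125, exactly the figure in Section 11.4. Equality would need two things: the ratio must equal 8 at the moment of stopping, and stopping must be certain at the 20% rate. Neither holds here. The ratio can cross 8 only when a toxicity occurs, and each toxicity multiplies it by 4, so it usually lands well above 8. Monitoring also ends at 36 patients.

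The sentence nevertheless attributes 1/8 to this boundary. This is the plan's only formal statistical stopping rule for safety, and its single stated property would not be the one it has. A reader would think the rule more prone to false alarms than it is. Section 11.3, by contrast, reports the attained errors of the response test (0.09 and 0.09) beside the 10% targets.

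**Working it through.** **Inputs, all from Section 11.4.** Permitted rate 0.05; unacceptable rate 0.20; stop when LR ≥ 8; a look after every patient, N = 1 to 36; the Table 1 entries listed above.

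**Step 1: reproduce Table 1.** With x toxicities in N patients,

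LR(x, N) = (0.20/0.05)^x × (0.80/0.95)^(N−x) = 4^x × 0.8421^(N−x).

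The table entry should be the smallest x with LR ≥ 8. At the points where the entry changes:

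| x / N | LR | x / N | LR |
|---|---|---|---|
| 2/6 | 8.05 | 2/7 | 6.78 |
| 3/15 | 8.14 | 3/16 | 6.85 |
| 4/24 | 8.23 | 4/25 | 6.93 |
| 5/33 | 8.33 | 5/34 | 7.01 |

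All 36 entries of Table 1 agree with the rule.

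**Step 2: reproduce the stated 0.125.** 1/k = 1/8 = 0.125. This is the general ceiling and uses neither Table 1 nor the cap at 36.

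**Step 3: the attained rate.** Assume each patient's outcome is known before the next look. Carry the distribution of the cumulative count forward one patient at a time: P(x at N) = (1−p) × P(x at N−1) + p × P(x−1 at N−1). Remove, and add to the stopping probability, any mass that reaches the Table 1 entry.

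The first segment can be checked by hand. For N = 1 to 6 the study stops if two or more toxicities occur, so at p = 0.05 the probability is 1 − 0.95^6 − 6 × 0.05 × 0.95^5 = 1 − 0.73509 − 0.23213 = 0.03277 (from unrounded terms). Continuing the recursion at p = 0.05:

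| Patients | Probability of stopping in this segment |
|---|---|
| 1–6 | 0.03277 |
| 7–15 | 0.02268 |
| 16–24 | 0.01158 |
| 25–33 | 0.00636 |
| 34–36 | 0.00027 |
| **Total** | **0.07366** |

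The same recursion at p = 0.20 gives 0.8731. A simulation of 400,000 trials at p = 0.05 gives 0.0735.

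**Step 4: why it falls short of 1/8.** At stopping, LR ranges from 8.05 to 28.05, with a mean of 11.85 when the true rate is 5%. By the likelihood-ratio identity,

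P(stop at 5%) = P(stop at 20%) / mean LR at stopping = 0.8731 / 11.85 = 0.0737,

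which agrees with the recursion. If the ratio landed exactly on 8, the same cap at 36 would give 0.8731 / 8 = 0.109. Most of the gap is therefore overshoot. Consistently, with the cap lifted and the LR ≥ 8 rule run to N = 1000, the 5% figure is 0.0835.

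**Step 5: other readings.** Requiring more than the tabulated count gives 0.0127 at 5%. A single look at N = 36 (6 or more toxicities) gives 0.0083. Neither comes near 0.125.

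**The case against.** The best defence is that 1/k is the usual approximation for a likelihood-ratio boundary when overshoot is ignored, and that the sentence says the rate is approximate. It is also a safe figure: the true rate cannot exceed it. The operative instruction is the LR ≥ 8 rule and its table, both right, and the 0.125 feeds no sample size, efficacy test or other calculation.

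Most of this stands and fixes the weight of the point: it is minor. What does not stand is that the qualifier covers the gap. The stated value is 0.125/0.074 = 1.7 times the attained one, and the sentence claims to describe this particular boundary.

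Some stronger readings are tempting, and the documents do not support them.

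- A reader might infer that the boundary was miscalculated. It was not: every entry follows from LR ≥ 8.
- A reader might infer that a false-stop rate below 0.125 leaves participants less protected than planned. The plan defines the rule by strength of evidence and does not set 0.125 as a target, and the rule stops with probability 0.87 at the rate it is meant to detect.
- A reader might fault the rule for stopping only about one time in three (0.35) at a true 10%. That is ordinary behaviour at a rate between the two hypotheses, and the plan sets no target there.
- A reader might think the counted event undefined. Sections 4.1 and 11.2 give extended grade 4 toxicity a duration of one week or more.

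The absence of a stopping probability at 20% contradicts nothing in the plan. Supplying it is a useful addition, not the correction of an error.

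**Conclusion.** The point holds as a misstatement of one operating characteristic. The figure of about 1/8 is an upper bound; the Table 1 boundary stops within 36 patients with probability 0.074 at a true rate of 5%, and 0.87 at 20%. The stated value errs on the conservative side, and no boundary value or stopping decision changes.

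The attained figures assume independent patients with a common toxicity rate, stopping as soon as the count reaches the Table 1 entry, and each outcome known before the next look. If some outcomes are still outstanding when the count is read against the number accrued, the known count can only be lower, so the stopping probability cannot rise above these values. The conclusion that 0.125 is not attained does not depend on prompt outcomes.

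**What to change.** Replace the sentence on erroneous stopping in Section 11.4 with:

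> The rate of erroneously stopping is at most 1/8; if each patient's outcome is known before the next look, the probability of stopping within 36 patients is 0.07 at a true rate of 5% and 0.87 at 20%.

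The cost is one sentence. Table 1, the LR ≥ 8 threshold, the sample size and the conduct of monitoring all stay as they are.
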